**13.2 Describe what data will be collected.**

*NOTE: For studies with multiple data collection points or long-term follow up, consider the addition of a schedule or table in your response.*

**Response:**

- Demographic (patient name, age, sex)
- Canine Retraction Rate (mm/month)
- Position of Canine T0-T4
- Total retraction distance (mm)

**13.3 List any instruments or measurement tools used to collect data (e.g. questionnaire, interview guide, validated instrument, data collection form).**

*Include copies of these documents with your submission.*

**Response:** Data collection spreadsheet is uploaded in Click. Intraoral 3D scans of the upper arch via iTero scanner

**13.4 Describe any source records that will be used to collect data about subjects (e.g. school records, electronic medical records).**

**Response:** Patient data will be pulled from the University at Buffalo School of Dental Medicine EMR database as well as the Orthodontic Department at the SDM record systems. Systems used are:

- Dolphin (used for imaging storage: photographs and radiographs)
- OrthoCad (used for 3D model storage)
- AXIUM – (medical, dental and treatment history database – EMR software)

**13.5 Indicate whether or not **individual** subject results, such as results of investigational diagnostic tests, genetic tests, or incidental findings will be**

*shared with subjects or others (e.g., the subject's primary care physician) and if so, describe how these will be shared.*

**Response:** If there are any clinical findings relating to the subject's dental health will be shared with the subject and guardian and will also be notified to their primary care provider when necessary, as per SOC protocols. If any anecdotal findings arise, they will be mentioned to the subject and guardians as well.

*13.6 Indicate whether or not study results will be shared with subjects or others, and if so, describe how these will be shared.*

**Response:** If the subjects wish to know the results of the study they will be notified in person once all data results have been calculated and analyzed. Aggregated study results can potentially be presented at conferences and / or published in journal articles.

## 14.0 Study Timelines\*

*14.1 Describe the anticipated duration needed to enroll all study subjects.*

**Response:** 6 months (from screening to recruitment into the study)

*14.2 Describe the duration of an individual subject's participation in the study. Include length of study visits, and overall study follow-up time.*

**Response:** The study will last during a specific portion of the patient's treatment; it will finish before the patient's treatment has been completed. They will have followed up visits to finish their orthodontic treatment. The full duration of the study will be four months. Initial records will be collected at T0. T1 will be the beginning of study, with adjustment and data collection happening every four weeks. Final records will be collected at T4.

*14.3 Describe the estimated duration for the investigators to complete this study (i.e. all data is collected and all analyses have been completed).*

**Response:** 14 months

## 15.0 Setting

*15.1 Describe all facilities/sites where you will be conducting research procedures. Include a description of the security and privacy of the facilities (e.g. locked facility, limited access, privacy barriers). Facility, department, and type of room are relevant. Do not abbreviate facility names.*

*NOTE: Examples of acceptable response may be: "A classroom setting in the Department of Psychology equipped with a computer with relevant survey administration software," "The angiogram suite at Buffalo General Medical Center, a fully accredited tertiary care institution within New York State with badge access," or, "Community Center meeting hall."*

**Response:** The facility where the study will be conducted is the Orthodontics Department at the University at Buffalo School of Dental Medicine. The facility has individual operatories (twenty total) for residents to administer orthodontic treatment. Each operatory is equipped with all standard of care equipment and necessary tools to treat patients in full orthodontic capacity. The entire facility and all of the computer systems are equipped with encrypted login devices connected to each operatory computer. Each computer can only be accessed via university issued identification badges, once activated each individual has to input their credentials to access our patient management software, AXIUM. Orthodontic department patients can only be viewed by faculty, staff and residents in the department, all others are restricted from accessing. Patient electronic health records along with schedules are not left open while treating patients to avoid any neighboring patients view of other's personal information. The computers after thirty minutes of idle will automatically log the individual off for security purposes. Any input to the patient's electronic health record, notes, diagnostic codes, treatment plans, etc., have to fully be reviewed by the supervising faculty prior to dismissal of the patient. The facility is restricted to faculty, staff and residents of the Orthodontic Department. No other individuals have access to the facility, and patients are only allowed to enter accompanied by resident or faculty during appropriate clinic operating hours and supervision. The facility is otherwise locked outside of clinic hours and restricted only to the custodian staff overnight and on the weekends. Our intraoral 3D scanner has its own operatory in a designated corner of the facility with appropriate barriers and positioning of the iTero scanner to prevent disclosure of private sensitive information to those around. There is a designated computer laboratory for residents and faculty to work on research projects, data analysis, treatment planning, and for educational purposes. Only a certain amount of people is allowed in the room and there is spacing between individual computers so that there is adequate space between users. The same security measures are present for the computers in the laboratory as in the operatories.

15.2 *For research conducted outside of UB and its affiliates, describe:*

- *Site-specific regulations or customs affecting the research*
- *Local scientific and ethical review structure*

*NOTE: This question is referring to UB affiliated research taking place outside UB, i.e. research conducted in the community, school-based research, international research, etc. It is not referring to multi-site research. UB affiliated institutions include Kaleida Health, ECMC, and Roswell Park Cancer Institute.*

**Response:**

**N/A:** This study is not conducted outside of UB or its affiliates.

## 16.0 Community-Based Participatory Research

16.1 *Describe involvement of the community in the design and conduct of the research.*

*NOTE: Community-Based Participatory Research (CBPR) is a collaborative approach to research that equitably involves all partners in the research process and recognizes the unique strengths that each brings. CBPR begins with a research topic of importance to the community, has the aim of combining knowledge with action and achieving social change to improve health outcomes and eliminate health disparities.*

Response:

**N/A:** This study does not utilize CBPR.

16.2 *Describe the composition and involvement of a community advisory board.*

Response:

**N/A:** This study does not have a community advisory board.

***Describe other resources available to conduct the research.***

**17.2** *Describe the time and effort that the Principal Investigator and research staff will devote to conducting and completing the research.*

*NOTE: Examples include the percentage of Full Time Equivalents (FTE), hours per week. The question will elicit whether there are appropriate resources to conduct the research.*

**Response:** The time that will be allotted to research will be equivalent to 8 FTE hours per week. This time will be utilized to:

- Develop the appropriate archwire system to facilitate a split mouth design with the intervention and control group
- Collect, store and organize all records and data for each subject
- Perform necessary orthodontic adjustments for each patient
- Analyze data collected and work on the statistical analysis

**17.3** *Describe the availability of medical or psychological resources that subjects might need as a result of anticipated consequences of the human research, if applicable.*

*NOTE: One example includes: on-call availability of a counselor or psychologist for a study that screens subjects for depression.*

**Response:** The design of the study maintains minimal risk given that the orthodontic treatment is routine and there will not be a substantial increase in risk. All patients will have access to all resources they might need. If there are questions or concerns, they will have the Orthodontic department's emergency hotline, which will be able to route them to the appropriate individual that can help them. There are emergency procedures in place as well which they can access if necessary, during any time in the treatment. If the patient experiences

any psychological issues there are resources available which can easily be accessed.

*17.4 Describe your process to ensure that all persons assisting with the research are adequately informed about the protocol, the research procedures, and their duties and functions.*

**Response:** The entire protocol will be available in hard copy and electronic copy for anyone who will be involved in the research study. A streamlined version of the protocol will also be available for all who will be involved. There will be a presentation before patient recruitment commences to ensure that everyone who is involved can ask any questions and understands the workflow of the protocol. During this presentation, the duties and responsibilities of those who are involved will be explained and addressed.

## **18.0 Other Approvals**

*18.1 Describe any approvals that will be obtained prior to commencing the research (e.g., school, external site, funding agency, laboratory, radiation safety, or biosafety).*

**Response:**

**N/A:** This study does not require any other approvals.

## **19.0 Provisions to Protect the Privacy Interests of Subjects**

*19.1 Describe how you will protect subjects' privacy interests during the course of this research.*

*NOTE: Privacy refers to an individual's right to control access to him or herself. Privacy applies to the person. Confidentiality refers to how data collected about individuals for the research will be protected by the researcher from release. Confidentiality applies to the data.*

*Examples of appropriate responses include: "participant only meets with a study coordinator in a classroom setting where no one can overhear", or "the participant is reminded that they are free to refuse to answer any questions that they do not feel comfortable answering."*

**Response:** All participants will be communicated to in a private office enclosed setting where there will be no one else to overhear what is discussed. The participants will only be meeting with research examiner and supervising faculty. The participants at any point are free to refuse treatment and anything during treatment that they do not feel comfortable with and leave the study at their own discretion.

*19.2 Indicate how the research team is permitted to access any sources of information about the subjects.*

*NOTE: Examples of appropriate responses include: school permission for review of records, consent of the subject, HIPAA waiver. This question **does apply** to records reviews.*

**Response:** Patients will be screened for eligibility for the study, after they have been diagnosed in clinic and treatment planned. We will be utilizing a partial HIPAA Waiver (HRP-611) for the purposes of pre-screening records. Once they have agreed to enroll, children will sign an assent form and their parents will sign an informed consent with HIPAA Authorization.

## 20.0 Data Management and Analysis\*

*20.1 Describe the data analysis plan, including any statistical procedures. This section applies to both quantitative and qualitative analysis.*

**Response:** Statistical analysis will be performed using the Statistical Package for the Social Sciences (SPSS). To assess normality of all quantitative variable distributions the Shapiro-Wilk Test will be utilized. To evaluate statistical significance in the difference between experimental and control groups for preoperative and postoperative measurements, a paired t-test will be used. The level of significance will be set to  $p \leq 0.05$  and to assess inter- and intraobserver reliability the intraclass correlation coefficients were obtained.

*20.2 If applicable, provide a power analysis.*

*NOTE: This may not apply to certain types of studies, including chart/records reviews, survey studies, or observational studies. This question is asked to elicit whether the investigator has an adequate sample size to achieve the study objectives and justify a conclusion.*

**Response:** Sample size estimation: Based on a power of 80% and a significance level of 0.05, it was determined that a sample of size of 16 would be sufficient to detect a difference of 0.5mm or greater.

*20.3 Describe any procedures that will be used for quality control of collected data.*

**Response:** The research examiner and supervisors will be ensuring that the data is good quality and is adequate for analysis. All patient records and data will be encrypted, deidentified and properly stored and secured on our computer network.

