## 8.0 Local Number of Subjects

8.1 *Indicate the total number of subjects that will be enrolled or records that will be reviewed locally.*

**Response:** 16 patients

8.2 *If applicable, indicate how many subjects you expect to screen to reach your target sample (i.e. your screen failure rate).*

**Response:** 60-70 patients

8.3 *Justify the feasibility of recruiting the proposed number of eligible subjects within the anticipated recruitment period. For example, how many potential subjects do you have access to? What percentage of those potential subjects do you need to recruit?*

**Response:** We will be collaborating with the entire patient pool in our orthodontic residency clinic for the first- and second-year residents. Research examiner will instruct residents doing patient screenings and acceptance of patients on criteria necessary to become a subject in the current study. Research examiner will then evaluate all eligible subjects and see if they meet all inclusion criteria and proceed to inform the subjects of their eligibility and purpose of the study. Each resident can screen approximately 20-30 patients in the course of 2-3 months. If we utilize the patient pools of twelve residents, we can approximate 240 patients total of which the study needs only 6.67% of to get 16 subjects.

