**Response:**

- Systemic diseases or syndromes,
- abnormalities in tooth shape and/or size,
- previous orthodontic treatment,
- medications that can affect the outcome of the study,

- craniofacial anomalies,
- periodontal disease or attachment loss,
- significant root resorption prior to or during the study (more than 1/3rd root length).
- Patients with known allergy to nickel

9.3 *Indicate specifically whether you will include any of the following special populations in your study using the checkboxes below.*

**NOTE: Members of special populations may not be targeted for enrollment in your study unless you indicate this in your inclusion criteria.**

Response:

- Adults unable to consent
- Individuals who are not yet adults (infants, children, teenagers)
- Pregnant women
- Prisoners

9.4 *Indicate whether you will include non-English speaking individuals in your study. Provide justification if you will exclude non-English speaking individuals.*

*In order to meet one of the primary ethical principles of equitable selection of subjects, non-English speaking individuals may **not** be routinely excluded from research as a matter of convenience.*

*In cases where the research is of therapeutic intent or is designed to investigate areas that would necessarily require certain populations who may not speak English, the researcher is required to make efforts to recruit and include non-English speaking individuals. However, there are studies in which it would be reasonable to limit subjects to those who speak English. Some examples include pilot studies, small unfunded studies with validated instruments not available in other languages, studies with numerous questionnaires, and some non-therapeutic studies which offer no direct benefit.*

**Response:** We will not be including Non-English-speaking subjects. All of the treatment is available as Standard of Care and no potential benefits would be inequitably withheld from Non-English-speakers.

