## **22.0      Withdrawal of Subjects\***

**N/A:** This study is not enrolling subjects. This section does not apply.

*22.1 Describe anticipated circumstances under which subjects may be withdrawn from the research without their consent.*

**Response:** If the subjects:

- Develop any indication of root resorption
- Develop any periodontal issues during the course of the study
- Develop any health-related issues during the study
- Voluntarily want to leave the study or cease treatment
- Do not come regularly as needed for the study

*22.2 Describe any procedures for orderly termination.*

*NOTE: Examples may include return of study drug, exit interview with clinician. Include whether additional follow up is recommended for safety reasons for physical or emotional health.*

**Response:** The subjects may withdraw their consent and discontinue their participation at any time. At which point, all collected data of the subject will be destroyed and discarded accordingly.

*22.3 Describe procedures that will be followed when subjects withdraw from the research, including retention of already collected data, and partial withdrawal from procedures with continued data collection, as applicable.*

**Response:** If subjects withdraw from the research, their data will not be used in the research study as the data will not be complete. It will be destroyed and discarded accordingly. The IRB correspondence and signed consent forms from withdrawn subjects will be maintained for 3 years.

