## 28.0 Consent Process

28.1 *Indicate whether you will be obtaining consent.*

*NOTE: This does not refer to consent documentation, but rather whether you will be obtaining permission from subjects to participate in a research study. Consent documentation is addressed in Section 27.0.*

**Yes** (*If yes, Provide responses to each question in this Section*)

**No** (*If no, Skip to Section 27.0*)

28.2 *Describe where the consent process will take place. Include steps to maximize subjects' privacy.*

**Response:** Consent will take place at the University at Buffalo School of Dental Medicine in the Orthodontic Department. Specifically, this will take place in the privacy of a faculty office which will be completely closed and private. Patients will be able to ask their questions and concerns with absolute privacy.

*28.3 Describe how you will ensure that subjects are provided with a sufficient period of time to consider taking part in the research study.*

*NOTE: It is always a requirement that a prospective subject is given sufficient time to have their questions answered and consider their participation. See “SOP: Informed Consent Process for Research (HRP-090)” Sections 5.5 and 5.6.*

**Response:** Patients will be allotted appropriate time to discuss amongst themselves and appropriate parent / guardians with or without the research examiner present, whichever they prefer. If subjects need more time to think and discuss outside of the clinic and come back at a later time to make their decision to participate this is acceptable. Patients can take as long as needed to make their decision and voice their concerns, there will be no time restriction or pressure from the research team.

*28.4 Describe any process to ensure ongoing consent, defined as a subject’s willingness to continue participation for the duration of the research study.*

**Response:** Patients will be asked at every visit if they wish to continue in their current research study. Patient will have full autonomy to withdraw or continue. There will be appropriate documentation that will be signed by the patient to ensure consent was given.

*28.5 Indicate whether you will be following “SOP: Informed Consent Process for Research (HRP-090).” Pay particular attention to Sections 5.4-5.9. If not, or if there are any exceptions or additional details to what is covered in the SOP, describe:*

- *The role of the individuals listed in the application who are involved in the consent process*

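### Does the 80% power claim for 16 patients fail because withdrawn patients are discarded and no allowance for loss is stated?

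*Combined protocol and SAP*

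**What the plan says.** Section 20.2 gives the whole sample size argument in one sentence. Taking alpha as 0.05 and aiming for 80% power, the plan reports that "it was determined that a sample of size of 16 would be sufficient to detect a difference of 0.5mm or greater". It gives no SD of the within-patient difference and no sidedness. It does not say whether the 0.5 mm refers to total retraction or to a monthly rate, or whether 16 counts enrolled or completing patients. The test is named next door in 20.1, where "a paired t-test will be used".

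The study summary (2.0) and section 8.1 both put the number of patients at 16. Section 8.3 works to the same target, saying that "the study needs only 6.67% of to get 16 subjects" (16/240 = 6.67%). The 60 to 70 patients in 8.2 are those to be screened, not a surplus to be enrolled.

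Section 22.1 lists grounds for withdrawal, including patients who "Do not come regularly as needed for the study". On withdrawal, 22.2 says that "all collected data of the subject will be destroyed and discarded accordingly", and 22.3 says that "their data will not be used in the research study as the data will not be complete". No section provides for replacement or extra enrolment.

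**The concern.** The number said to be sufficient equals the number to be enrolled, while the plan foresees withdrawals and keeps nothing from them. In a split-mouth trial each withdrawal removes a complete pair. If 16 has no slack, the trial reaches its stated power only when nobody leaves. A reader of a non-significant result might then credit the trial with 80% power for 0.5 mm when it had less.

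**Working it through.** **Inputs.** From the plan: n = 16, power 80%, significance level 0.05, difference 0.5 mm (20.2); paired t-test (20.1); one pair per patient (6.1). Not in the plan: the SD of the within-patient difference, the sidedness and any rate of loss. These are treated as assumptions. Section 3.2 states a directional hypothesis, so both one-sided and two-sided results are given.

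**Formula.** With d = 0.5/SD, two-sided power at n pairs is P(T > t*) + P(T < −t*). Here T is non-central t with n − 1 degrees of freedom and non-centrality d√n, and t* is the 97.5% point of the central t. The one-sided version uses the upper tail and the 95% point.

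**The plan's own figure.** Without an SD, 16 cannot be reproduced forwards, so the formula is solved backwards:

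- 80% at n = 16 needs d = 0.7495, so SD = 0.5/0.7495 = 0.667 mm.
- 80% at n = 15 needs d = 0.7780, so SD = 0.5/0.7780 = 0.643 mm.

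So 16 is the smallest n giving 80% only if the SD is above 0.643 and at most 0.667 mm, a band of 0.667 − 0.643 = 0.024 mm. One-sided, d is 0.6517 and 0.6755, and the band runs from 0.740 to 0.767 mm.

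**Two-sided power (%) by number of completing pairs.**

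| SD (mm), assumed | 16 | 15 | 14 | 12 | smallest n for 80% |
|---|---|---|---|---|---|
| 0.50 | 96.2 | 94.9 | 93.2 | 88.3 | 10 |
| 0.60 | 87.6 | 85.1 | 82.2 | 74.8 | 14 |
| 0.643 (lower limit) | 82.8 | 80.0 | 76.8 | 69.0 | 15 |
| 0.667 (upper limit) | 80.0 | 77.0 | 73.7 | 65.8 | 16 |
| 0.70 | 76.1 | 73.0 | 69.6 | 61.6 | 18 |
| 0.80 | 64.7 | 61.5 | 58.1 | 50.6 | 23 |

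If one-sided power is exactly 80% at 16, it is 77.5% at 15, 74.7% at 14 and 68.1% at 12.

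**Reading the table.** Three cases arise.

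1. SD of 0.643 mm or less: one loss leaves 80% or more. At 0.60 mm, even two losses leave 82.2%.
2. SD within the band: the first loss takes power below 80%, by at most 80.0 − 77.0 = 3.0 points.
3. SD above 0.667 mm: 80% is missed with no loss at all, so withdrawals are not the cause.

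Only the second case supports the concern, and nothing in the plan points to it.

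**Relative size.** With all 16 completing, moving the assumed SD from 0.60 to 0.80 mm costs 87.6 − 64.7 = 22.9 points. The first loss costs about 3.

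**How likely a loss is.** The plan gives no rate. If each patient is lost independently with probability q, all 16 complete with probability (1 − q)^16. This is 0.724, 0.440 and 0.185 at assumed q of 2%, 5% and 10%. Expected losses, 16q, are 0.3, 0.8 and 1.6 patients. Some loss is plausible, but many losses are not implied.

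**What the discard rule adds.** Section 13.1 measures total retraction from T0 to T4. A patient who leaves before T4 has no such value to enter in the paired test, whether or not earlier scans are kept. The rule costs extra information only where partial data could be used, such as a rate over completed intervals.

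**The case for a change.** The best case for a change is that 20.2 makes a formal 80% claim despite the pilot label, and 3.2 states a hypothesis to be tested. Two or three sentences giving the SD and its source, the sidedness, the outcome, and power at 16, 14 and 12 completing pairs would let a reader judge a null result. No extra patients would be needed if 16 is the enrolled number.

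Much of this stands. The 80% cannot be checked from the plan, any slack for losses is undisclosed, and the missing SD matters more than the missing allowance. What does not stand is the inference that losses cause the stated power to be missed. Saying that one loss breaks 80% if 16 is the smallest n for 80% only restates what smallest means; 20.2 claims no more than sufficiency.

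Two supporting points are also weak. The statement in 28.4 that "Patients will be asked at every visit if they wish to continue in their current research study" is routine ongoing consent and predicts no particular loss. The exclusion in 9.2 for "significant root resorption prior to or during the study" is limited to more than a third of root length, while 22.1 withdraws for any sign of resorption. The first falls inside the second, so they are not two separate routes of loss. The two wordings differ and must be reconciled, but that is a separate matter from power.

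The unit of 16 in 20.2 is also unnamed. Sections 2.0 and 8.1 point to patients, and nothing supports counting sides. If sides were meant (8 pairs giving 80%), 16 patients would have about 99% power and 12 about 95%.

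**Conclusion.** No change to the plan follows. The omission is real, but it is a gap in documentation and the documents do not show that withdrawals defeat the stated power. If 16 patients give exactly 80%, the cost is about 3 points for one loss, 6 for two (80.0 − 73.7 = 6.3) and 14 for four (80.0 − 65.8 = 14.2). With a smaller SD there is slack; with an SD above 0.667 mm the shortfall exists without any loss. These figures assume a two-sided paired t-test at 0.05, a true difference of 0.5 mm and one pair per patient.

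The planned power does not enter the analysis. The analyst will run the paired comparison on completing patients and can report how many there were, with a confidence interval for the mean difference. That interval reflects the SD and number actually observed, and is a sounder basis for reading a null result than any planned power. A fuller 20.2 would be tidier, but it would leave the analysis, the results and the conclusions of this pilot as they are.
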